# 3.3.2.4 Recurrence of *Clostridium Difficile* Infection (*Clostridium Difficile* Infection Group Only)

The investigator or subinvestigator will assess the recurrence of CDI at FU2 or withdrawal according to the assessment criteria shown in Table 3.3-4 for patients who achieved "clinical cure" at the end of treatment.

Table 3.3-4 Assessment Criteria for Recurrence of *Clostridium Difficile* Infection

Assessment of Recurrence of CDI	Definition
Sustained cure	No recurrence
Recurrence	
 
Meeting all the following criteria
 
New episode of diarrhea is occurred in the period from the end of treatment to FU2 or withdrawal (liquid or unformed stools ≥ 3 times/day within 24 hours)
 

	Medication or therapy is required to treat CDI in the period from the end of treatment to FU2 or withdrawal
	A positive toxin A/B assay at FU2 or withdrawal (positive for either or both toxins)

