#### 4) Follow-up 2 (CDI group)

The problem in the treatment for CDI is its high recurrence rate. CDI responds to the treatment with MTZ or VCM but recurs in approximately 15% to 30% cases. CDI repeatedly recurs, which may result in hospitalization and treatment for a long period. In this trial, for exploratory confirmation of the effect of OPS-2071 to prevent recurrence, presence/absence of recurrence will be confirmed 28 days after the end of treatment (FU2: Day 38) or at withdrawal in patients who achieved "clinical cure" at the end of treatment in the CDI group.

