## 7.1.7.1 Clostridium Difficile Infection Group

- Collection of stool specimens (the following items will be tested by the microbiological laboratory)
  - Bacterial culture test
  - Toxin A/B assay
- Confirmation of IMP compliance until withdrawal
- Confirmation of patients' clinical symptoms until withdrawal (daily stool count, stool symptoms, bloody stool, fever, abdominal pain, nausea, and vomiting)
- Assessment of clinical response: to be performed only in case of withdrawal during the IMP administration period
- Assessment of recurrence of CDI: to be performed only in case of withdrawal after completing the IMP administration
- Clinical laboratory tests (hematology test, biochemistry test, and urinalysis)
- 12-lead ECG: to be performed only in case of withdrawal during the IMP administration period
- Vital signs (blood pressure, pulse rate, and body temperature)
- Physical examination
- Confirmation of adverse events
- Confirmation of concomitant drugs and therapies

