#### 11.1.4 Clinical per Protocol Set

The clinical per protocol set (CPPS) comprises those patients in the FAS for whom all scheduled examinations at all specified observation time points up until the end of treatment or withdrawal have been performed.

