**CPPS** 

3) Analysis Method

Analysis will be performed by dose in the proportion of patients judged as "clinical cure" at the end of treatment in CPPS.

Prepare the list of result of judgment on CDI recurrence at FU2 or withdrawal.

Calculate CDI recurrence rate at FU2 or withdrawal. CDI recurrence rate is the proportion of the patients judged as "recurrent" against evaluable patients except for those with missing data.

Recurrence rate (%) = 
$$\frac{\text{Patients judged as "recurrent"}}{\text{Evaluable patients except for those with missing data}} \times 100$$

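### A cured CDI patient who withdraws relapse-free before FU2 is scored as a sustained cure and kept in the denominator, so the recurrence rate understates 28-day recurrence

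*Protocol*

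**What the plan says.** Section 3.2, item 4, gives the purpose of the second follow-up visit, an exploratory look at prevention of recurrence: "presence/absence of recurrence will be confirmed 28 days after the end of treatment (FU2: Day 38) or at withdrawal". It sets this against recurrence of about 15% to 30% after metronidazole or vancomycin.

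Section 3.3.2.4 sets the time and the criteria for patients cured at the end of treatment: "The investigator or subinvestigator will assess the recurrence of CDI at FU2 or withdrawal according to the assessment criteria shown in Table 3.3-4". Table 3.3-4 has two outcomes. Recurrence requires three criteria together: new diarrhea, need for CDI treatment, and a positive toxin assay. The window for the first reads: "New episode of diarrhea is occurred in the period from the end of treatment to FU2 or withdrawal". Sustained cure is defined only as "No recurrence".

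The withdrawal procedures in Section 7.1.7.1 include: "Assessment of recurrence of CDI: to be performed only in case of withdrawal after completing the IMP administration". Section 7.2.2.4 has the result entered in the CRF.

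The analysis set is the CPPS, which under Section 11.1.4 takes FAS patients for whom "all scheduled examinations at all specified observation time points up until the end of treatment or withdrawal have been performed". Section 11.3.4.4 then says "Calculate CDI recurrence rate at FU2 or withdrawal", as the proportion judged recurrent "against evaluable patients except for those with missing data".

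**The concern.** The rate mixes patients observed for the full period with patients observed for a few days, and gives both the same weight as non-recurrences. Take a cured patient who leaves relapse-free on Day 13 and attends the withdrawal examination. That patient has a valid, non-missing result after about 3 days at risk. A patient who leaves the same day without the recurrence assessment has no result and drops out. Whether short follow-up counts as cure therefore depends on attendance at a visit.

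Recurrence is a secondary objective, and Section 3.2 invites comparison with published rates of 15% to 30%. In a dose-ranging trial, a dose with more relapse-free dropout after treatment would also show a lower recurrence rate for that reason alone.

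The protocol handles this differently elsewhere. Table 3.3-2, for microbiological outcome, has an unknown/indeterminate category and names withdrawal as a reason for using it. Table 3.3-4 has no counterpart.

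**Working it through.** **The plan's own figure.** Day 38 minus the last dosing day, Day 10, is 28 days, as Section 3.2 states. Counted from the end-of-treatment visit on Day 11 it is 27 days.

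**How the rule treats a relapse-free leaver.**
1. Cured at the end of treatment, so eligible for the recurrence assessment (Section 3.3.2.4).
2. Withdraws after completing dosing, so the assessment is made (Section 7.1.7.1) and the value is not missing.
3. Does not meet the recurrence criteria, so is a sustained cure (Table 3.3-4).
4. Examined up to the end of treatment, so remains in the CPPS (Section 11.1.4).
5. Result not missing, so remains in the denominator (Section 11.3.4.4).

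Relapse-free withdrawal is possible under several criteria in Section 9.2, such as the patient's wish or an adverse event.

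**Expected size.** From the protocol: a 28-day window, background recurrence of 15% to 30%, and a target of 10 CDI patients per dose. Assumed, because the protocol does not give them: a constant hazard, and a fraction *w* of cured patients who leave on day *t* after the end of treatment if they have not yet relapsed. With true 28-day risk *p*:

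expected reported rate = (1 − w)·p + w·[1 − (1 − p)^(t/28)]

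- p = 30%, w = 20%, t = 3: 1 − 0.70^(3/28) = 0.0375; 0.8 × 0.30 + 0.2 × 0.0375 = 0.247.
- p = 30%, w = 20%, t = 14: 1 − 0.70^(14/28) = 0.163; 0.24 + 0.2 × 0.163 = 0.273.
- p = 15%, w = 20%, t = 1 and t = 14: 12.1% and 13.6%.

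| True risk | Leaving relapse-free | Day 1 | Day 4 | Day 7 | Day 14 |
|---|---|---|---|---|---|
| 30% | 5% | 28.6% | 28.7% | 28.9% | 29.3% |
| 30% | 10% | 27.1% | 27.5% | 27.9% | 28.6% |
| 30% | 20% | 24.3% | 25.0% | 25.7% | 27.3% |
| 30% | 30% | 21.4% | 22.5% | 23.6% | 25.9% |
| 15% | 5% | 14.3% | 14.4% | 14.4% | 14.6% |
| 15% | 10% | 13.6% | 13.7% | 13.9% | 14.3% |
| 15% | 20% | 12.1% | 12.5% | 12.8% | 13.6% |
| 15% | 30% | 10.7% | 11.2% | 11.7% | 12.8% |

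With no such leavers the shift is zero. Otherwise it is downward.

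**One dose group as an example.** Suppose 10 cured patients, 2 recurrences on days 15 and 20, and 2 relapse-free withdrawals on day 4.
- As written: 2/10 = 20%.
- Kaplan-Meier at day 28: 1 − (7/8)(6/7) = 25%.
- Leavers all counted as recurrent: 4/10 = 40%.

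**A tempting alternative.** Dropping relapse-free leavers while keeping early relapsers gives a simple rate among patients with FU2 or a recurrence. With p = 30%, w = 20%, t = 14, the events are 0.24 + 0.0327 = 0.2727 and the denominator is 0.80 + 0.0327 = 0.8327. The ratio is 32.7%, which is biased upward.

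**The case against.** The protocol never names a 28-day recurrence rate. Each description of the endpoint adds withdrawal as an alternative time, so there is no internal contradiction. The word evaluable in the denominator is undefined and could be given content in the SAP, and Section 11.2 lets the sponsor decide on problematic patients. The endpoint is exploratory, no test or confidence interval is planned for it, and individual judgments will be listed. With 3 recurrences in 10 patients the exact 95% interval runs from about 7% to 65%, while a shift from 30% to 24.7% is about half a patient in ten.

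Much of this bears on size, and there it stands. It does not remove the point. The only reason Section 3.2 gives for the visit is confirmation 28 days after treatment, and a proportion over unequal follow-up cannot be read that way. An undefined word does not override an outcome table that gives these patients a valid result. Because the protocol itself fixes the outcome and the stated exclusion, this is a rule set badly rather than detail left for later.

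A reader might go further and infer that every patient leaving early lowers the rate. The text does not support that. A leaver who meets the criteria at withdrawal is an event under Table 3.3-4. Use of, or need for, other CDI treatment is itself a withdrawal criterion (Section 9.2, item 3, with Section 6.2.1, item 7), so some post-treatment withdrawals will be relapses.

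**Conclusion.** The concern holds for relapse-free withdrawals after treatment and before FU2, and for those only. Read as a 28-day risk, the reported rate is biased downward by them. At a true 30% with 20% leaving, the loss is about 2.7 points at day 14 and 5.3 points at day 3. At 5% leaving it is under 1.5 points, and with no such leavers it is nil. These figures rest on a constant hazard and on assumed withdrawal rates and times.

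It would be tempting to conclude that the trial's recurrence rate will be materially too low, or that dose comparisons will be distorted. The protocol gives no withdrawal rate or timing, overall or by dose, so neither follows. For a secondary, exploratory endpoint with about 10 patients per dose the consequence is moderate. The wording should still be corrected, since one or two leavers can visibly move a figure based on ten patients.

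**What to change.** In Table 3.3-4, limit sustained cure to patients followed without recurrence to the FU2 window, that is Day 35 or later (Day 38 with its 3-day allowance). Add a category, not assessable at 28 days, for relapse-free withdrawal before that. Recurrences found at withdrawal remain events.

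In Section 11.3.4.4, report recurrence by Kaplan-Meier at 28 days after the end of treatment. Censor relapse-free withdrawals, and date a confirmed recurrence by the recorded onset of the new diarrhea episode. Beside it give the range with early leavers counted all as not recurrent (the present rule) and all as recurrent. Do not report the simple rate among patients with FU2 or a recurrence on its own, because of the upward bias shown above.

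The cost is wording in one table and one analysis paragraph, plus one event-date rule, which is needed because recurrence is a three-part composite with no defined date. Diary entries and withdrawal dates are already recorded, so no new data are needed and patient care is unchanged. The resulting figure will be slightly higher and less precise where such leavers occur. Kaplan-Meier assumes that withdrawal is unrelated to relapse risk; the range covers departures from that.

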#### Secondary objectives:

- To assess the recurrence rate of CDI in patients with bacterial enteritis associated with CDI after multiple doses of OPS-2071.
- To assess the time to resolution of diarrhea in patients with bacterial enteritis associated with CDI or enteric infection after multiple doses of OPS-2071.
- To assess the improvement of clinical symptoms in patients with bacterial enteritis associated with CDI or enteric infection after multiple doses of OPS-2071.
- To assess the sensitivity to OPS-2071 of the causative pathogen strain isolated from patients with bacterial enteritis associated with CDI or enteric infection.

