# 3.3.2.3 Clinical Response

The investigator or subinvestigator will refer to the information from patients (eg, patient diary), and assess clinical response at the time of observation (Day 4 and end of treatment) according to the assessment criteria shown in Table 3.3-3.

Table 3.3-3 Assessment Criteria for Clinical Response

Clinical Response Assessment	Definition
Clinical cure	Meeting all the following criteria within 24 hours before observation  No liquid or unformed stool
	No abdominal symptoms and no other symptoms (fever, nausea, vomiting)
	No need of medication or therapy to treat CDI or enteric infection
Clinical improvement	Fulfilling at least one of the following criteria within 24 hours before observation  • Liquid or unformed stools ≤ 2 times/day
	No abdominal symptoms and no other symptoms (fever, nausea, vomiting)
	No need of medication or therapy to treat CDI or enteric infection
Clinical failure	Fulfilling none of the above-mentioned clinical improvement criteria.  Patients who received medication or therapy to treat CDI or enteric infection prior to the time of observation are to be assessed as "clinical failure".

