**CPPS** 

3) Analysis Method

Analysis will be performed by disease group and by dose, by causative strain, and by MIC values of OPS-2071 against the causative strain. Calculate frequency distribution at each evaluation time point and prepare a list of causative strains by patients.

Calculate the clinical response rate and 95% CI at each evaluation time point. Clinical response rate will be calculated as the proportion of the patients judged as "clinical cure" or "clinical improvement" against evaluable patients except for those with missing data.

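### CDI patients who only improve and then relapse enter no recurrence or sustained-response rate, and cured patients who leave early count as sustained cures

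*Protocol*

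**What the plan says.** The secondary objective (Protocol Section 2) is "To assess the recurrence rate of CDI in patients with bacterial enteritis associated with CDI after multiple doses of OPS-2071". It is not limited to patients who were cured.

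The endpoint is narrower. Section 3.3.2.4 assesses recurrence at follow-up 2 (FU2) or withdrawal by "Table 3.3-4 for patients who achieved 'clinical cure' at the end of treatment", and Section 7.2.2.4 repeats the restriction. Section 11.3.4.4 carries it into the analysis: "Analysis will be performed by dose in the proportion of patients judged as 'clinical cure' at the end of treatment in CPPS".

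Response is wider. Section 11.3.4.3 states: "Clinical response rate will be calculated as the proportion of the patients judged as 'clinical cure' or 'clinical improvement' against evaluable patients". In Table 3.3-3, cure requires no unformed stool, no need of treatment for the infection, and "No abdominal symptoms and no other symptoms (fever, nausea, vomiting"), all over the previous 24 hours. Improvement requires "Fulfilling at least one of the following criteria within 24 hours before observation", from a list of three.

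On timing, Section 7.2.2.3 judges response at Day 4, end of treatment and withdrawal, and Section 7.1.7.1 limits the last to withdrawal during dosing. Nothing re-judges response at follow-up.

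Table 3.3-4 defines sustained cure simply as absence of recurrence, judged at FU2 or withdrawal. Section 3.2, item 4, gives the aim as recurrence status 28 days after treatment. Section 7.2.2.4 sends the investigator to Table 3.3-3, the response table, for the recurrence criteria, which are in Table 3.3-4.

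**The concern.** Two groups of patients are handled in a way that does not serve the recurrence objective.

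The first is CDI patients who end treatment improved but not cured. The cure definition is strict: one unformed stool, or a fever or nausea from another cause, in the last 24 hours is enough to miss it. Section 6.2.2 allows continued antibiotics for an underlying disease, so such symptoms are plausible. These patients count towards efficacy at the end of treatment, but nothing that happens to them afterwards enters a planned rate. The recurrence denominator becomes the number cured, which can differ from dose to dose.

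The second is cured patients who leave after dosing but before FU2. They have a recurrence assessment at withdrawal, so they are not missing, and they count as non-recurrent after whatever follow-up they had.

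At stake is whether the trial can say, for each dose, how many CDI patients were well at Day 38. No test or error rate is involved, since the trial is descriptive.

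**Working it through.** **Inputs from the Protocol.** 10 CDI patients per dose (Section 3.4). Background recurrence 15% to 30%, quoted for metronidazole or vancomycin (Section 3.2, item 4). Last dosing day 10; FU2 on Day 38 ± 3 days (Table 7-1).

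**Assumed.** All 10 patients respond; I are improved, with I from 2 to 6, and C = 10 − I are cured. The Protocol gives no such split.

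1. *The plan's own figures.* 3 doses × 2 disease groups × 10 = 60, as in Section 3.4. Day 38 − Day 10 = 28 days, as in Section 3.2. Section 11.5 states that the size is not statistically derived, so there is no power figure to reproduce.

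2. *Follow one patient.* On Day 11 the patient has one unformed stool and needs no CDI therapy: not cure, but improvement, so a responder. On Day 20 diarrhea returns, CDI therapy is given and the toxin assay is positive. Section 9.2, criterion 3, requires withdrawal, and Section 7.1.7.1 provides culture and toxin assay at that point. All three conditions of Table 3.3-4 are met. The patient still counts in the response numerator, is in neither the numerator nor the denominator of the recurrence rate, and there is no sustained-response rate to enter.

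3. *Expected uncounted relapses per dose = I × r.*
   - r = 0.15: 2 × 0.15 = 0.3; 6 × 0.15 = 0.9.
   - r = 0.30: 2 × 0.30 = 0.6; 6 × 0.30 = 1.8.

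4. *Denominator.* C = 8 (I = 2) down to 4 (I = 6), instead of 10 responders.

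5. *Effect on the recurrence percentage.* The planned rate estimates r_c, the relapse rate in cured patients. The rate in all responders is (C × r_c + I × r_i) / 10.
   - If r_i = r_c, the two are equal: no bias.
   - If r_c = 0.15 and r_i = 0.30 (assumed): (8 × 0.15 + 2 × 0.30) / 10 = 18%; (4 × 0.15 + 6 × 0.30) / 10 = 24%; the planned rate reads 15%.

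6. *Effect on a reader's picture of sustained response.* Subtracting the counted recurrences from the responders gives (10 − C × r) / 10; the true value with equal relapse rates is 1 − r.
   - r = 0.15: 0.88 (C = 8) or 0.94 (C = 4), against 0.85.
   - r = 0.30: 0.76 (C = 8) or 0.88 (C = 4), against 0.70.

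   So the picture is too favourable even when the recurrence percentage is unbiased, and more so at a dose with fewer cures.

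7. *Early leavers.* A cured patient who withdraws well on Day 15 has 15 − 10 = 5 of the 28 days. Section 11.3.4.4 excludes only missing data, and this patient has an assessment. With R recurrences among C cured patients, one of whom is such a leaver, the planned rate is R / C against R / (C − 1) among those with a known outcome, a ratio of (C − 1) / C: 7/8 = 0.875 for C = 8, and 3/4 = 0.75 for C = 4.

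**The case against.** The strongest reply is that the restriction to cured patients is deliberate and coherent. It appears in the same form in the synopsis and in Sections 3.2, 3.3.2.4, 7.2.2.4 and 11.3.4.4, and the purpose is called exploratory. A patient with residual symptoms has not clearly recovered, so a new episode is hard to define. This stands: the plan does not contradict itself here, and the cure-only rate is a legitimate quantity.

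A reader might infer that the cure restriction biases the recurrence rate downward. The document does not support that. It would need improved patients to relapse more often than cured ones, and no such rates are given. The 15% to 30% figure is also for other drugs, not OPS-2071.

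A reader might also infer that these relapses are hidden. They are not. Symptoms and concomitant therapy are recorded through follow-up, toxin is assayed at FU2 or at withdrawal, and the frequency distribution in Section 11.3.4.3 shows cure and improvement separately by dose. Nor is the lasting responder label peculiar to improved patients: a cured patient who relapses also remains an end-of-treatment responder, but is counted as a recurrence.

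On early leavers, detailed evaluability rules may sit in the SAP. But the Protocol itself defines sustained cure at withdrawal without any minimum follow-up, and that definition is what investigators will apply.

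**Conclusion.** The concern holds as an endpoint-design weakness in an exploratory secondary objective, not as an error or contradiction. Two effects of the cure restriction follow from the text: any relapse in an improved patient goes uncounted, and the denominator is smaller and can vary by dose. Under the assumed split of 2 to 6 improved among 10 responders, and the cited 15% to 30%, that is 0.3 to 1.8 expected relapses per dose and a denominator of 8 to 4. The direction of any change in the recurrence percentage is unknown.

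The treatment of early leavers is a separate and more definite defect. It sits badly with the stated 28-day aim and can only lower the rate; how much depends on the number of early leavers, which cannot be known in advance.

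It would be going too far to assume that every CDI patient is available at FU2. Those given CDI therapy are withdrawn and have the withdrawal examination, so any added analysis must draw on both visits.

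**What to change.** Keep the cure-only recurrence rate. In Section 11.3.4.4 add, by dose:

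- **(a)** a supplementary recurrence rate, applying the criteria of Table 3.3-4 to end-of-treatment responders with at most 2 unformed stools/day and no CDI therapy. The stool limit is needed because meeting any single improvement criterion suffices, so a patient with 3 or more unformed stools can be labelled improved. Such patients stay outside this set, and the text should say so;
- **(b)** sustained response at Day 38: those same responders without recurrence through the FU2 window, divided by all treated CDI patients. This denominator does not depend on how many were cured.

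Count as sustained only patients followed to the FU2 window (Day 38 − 3 = Day 35 or later). Treat earlier withdrawals without recurrence as not assessable in the recurrence rate, or censor them in a time-to-recurrence summary. Censoring uses their partial follow-up. Excluding them while keeping early relapses can push the rate upward.

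In Section 7.2.2.4, change the reference from Table 3.3-3 to Table 3.3-4.

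Cost: wording and one more table. No new visit or sample is needed, because symptoms, therapy and toxin results are already collected at FU2 or withdrawal. The reported figures may be less favourable, and some improved patients will have residual symptoms, which is why the cure-only rate should stay beside the new ones. The rules should be fixed in advance, since the trial is open-label and recurrence is judged by the investigator.

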#### CDI group:

- 6. The patient satisfies both the following:
  - ✓ Liquid or unformed stools  $\ge 3$  times/day within 24 hours before the start of IMP administration
  - ✓ A positive clinical laboratory result in one of the following methods to confirm CDI within 48 hours before the start of IMP administration:
    - Toxin A/B assay (positive for either or both toxins A and B)
    - PCR (detection of toxin genes)
    - Colonoscopy (findings of pseudomembranous colitis)

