# 7.1.7 Time of Withdrawal and Withdrawal Examination: Allowance ± 2 Days

The investigator or subinvestigator will perform the following examination, observation, and assessments for patients who withdrew from the trial within 2 days after the day when withdrawal is considered necessary. If the patient refuses to undergo any examinations at the time of withdrawal, or if the investigator or subinvestigator judges that any examinations at the time of withdrawal cannot be performed due to an emergency or other circumstances (eg, SAE or recurrence of CDI), of the examination items specified for the time of withdrawal, only those items that can be performed will be performed. Results of tests and assessment, the date of measurements and assessment,

and the date of blood/urine/stool sampling will be recorded in the source records and CRF.

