## 7.2.2.2 Toxin A/B Assay

#### 1) Timing

CDI group: screening, Day 4, Day 11 (end of treatment), at FU2 (Day 38), at the time of withdrawal

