### 3) Method of Evaluation

The investigator or subinvestigator will record the sampling date in source documents and CRF. The sponsor will collect the toxin A/B assay result only of the CDI group tested at the microbiological laboratory. Use the result of toxin A/B assay from the microbiological laboratory.

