#### 2) Method of Confirmation

The investigator or subinvestigator will assess the recurrence of CDI at FU2 or withdrawal according to the assessment criteria shown in Table 3.3-3 for patients who achieved "clinical cure" at the end of treatment. The investigator or subinvestigator will record the assessment date and result in source documents and CRF.

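### A treated CDI recurrence with no positive central toxin result can be scored as sustained cure or drop out, and 7.1.7 lists recurrence itself as a reason for omitting the withdrawal tests

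*Protocol*

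**What the plan says.** **Definition.** Protocol 3.3.2.4, Table 3.3-4, applies to CDI patients with clinical cure at the end of treatment. Recurrence means "Meeting all the following criteria": a new episode of diarrhoea after the end of treatment, CDI therapy required in that period, and "A positive toxin A/B assay at FU2 or withdrawal (positive for either or both toxins". Sustained cure is defined only as the absence of recurrence.

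**Which result counts, and when it is taken.** Section 7.2.2.2 says: "Use the result of toxin A/B assay from the microbiological laboratory". Its timing is "CDI group: screening, Day 4, Day 11 (end of treatment), at FU2 (Day 38), at the time of withdrawal". After the end of treatment the assay is therefore scheduled only at FU2 and at withdrawal. FU1 (7.1.5.4) collects no stool.

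**What happens when CDI therapy is needed.** Other CDI treatment is prohibited until the end of the trial (6.2.1, item 7). Its use, or a judgement that it is required, leads to withdrawal (9.2, item 3).

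**What may be left out at withdrawal.** The withdrawal examination takes place within 2 days after withdrawal is judged necessary. It may be reduced to the feasible items if the patient refuses tests or they cannot be done "due to an emergency or other circumstances (eg, SAE or recurrence of CDI".

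**Analysis.** In 11.3.4.4, "CDI recurrence rate is the proportion of the patients judged as" recurrent, over evaluable patients without missing data. Section 11.2 rules out imputation. The CPPS (11.1.4) requires all scheduled examinations up to the end of treatment or withdrawal.

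**Cross-reference.** Section 7.2.2.4 tells the investigator to judge recurrence "according to the assessment criteria shown in Table 3.3-3 for patients who achieved" clinical cure. Table 3.3-3 is the clinical response table.

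**The concern.** The definition depends on one laboratory result. For a patient who relapses and is treated before Day 38, that result comes from the withdrawal visit. The protocol then names the event being measured as an acceptable reason for not taking the measurement. It also does not ask that the stool be collected before CDI therapy begins, so a sample taken up to 2 days after the decision may reflect treated disease.

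Table 3.3-4 has no category for treated diarrhoea without a toxin result. Read literally, the three conditions are not all met, so the patient is a sustained cure. Read through 11.3.4.4, the patient is missing and leaves the denominator. Either way a probable relapse is lost from the numerator.

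A related gap is that a cured patient who leaves before Day 38 without diarrhoea is assessed at withdrawal and can count as sustained cure without having completed the observation period.

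Section 3.2, item 4, calls the high recurrence rate the problem in CDI treatment, cites about 15% to 30% for MTZ or VCM, and gives exploration of recurrence prevention as the purpose of FU2. A definition that can only lose events bears directly on that purpose.

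**Working it through.** The protocol states no target or calculation for recurrence, so there is no figure to reproduce. The check is of the logic first, then of the direction and possible size.

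**1. Path of a treated relapse between Day 11 and Day 38**
- New diarrhoea: criterion 1 is met.
- CDI therapy required: criterion 2 is met, and 9.2 item 3 calls for withdrawal.
- The toxin assay is due at withdrawal (7.1.7.1), but 7.1.7 allows omission and lists recurrence as an example.
- Assay positive: recurrence.
- Assay negative, for instance because therapy had started: sustained cure.
- Assay not done: sustained cure if Table 3.3-4 is read literally. Otherwise the patient is excluded as missing under 11.3.4.4 and 11.2, or, on one reading, leaves the CPPS because a scheduled withdrawal examination was not performed.

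No rule in the protocol chooses between the outcomes of the last branch.

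**2. Direction**

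Let n be the number of clinical cures, R the true recurrences and k those without a positive central result.
- Scored as cure: (R − k)/n, which is below R/n for any k > 0.
- Dropped: (R − k)/(n − k). This is below R/n when n(R − k) < R(n − k), that is when R < n, so whenever at least one patient did not recur.

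Both routes lower the rate.

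**3. Counts**

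Ten CDI patients per dose are planned (3.4, 11.5). Ten cures is therefore an upper bound for the planned number, since only clinical cures are assessed. Take R = 3:
- k = 1: 2/10 = 20% or 2/9 = 22%, against 3/10 = 30%.
- k = 2: 1/10 = 10% or 1/8 = 12.5%.

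**4. Expected rates**

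True rate r = 15% to 30% (3.2, item 4). The share m of true recurrences without a positive central result is an assumption, shown at 20% and 50%; no value appears in the documents. The formulas are r(1 − m) if scored as cure and r(1 − m)/(1 − rm) if dropped.

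| r | m | Scored as cure | Dropped |
|---|---|---|---|
| 30% | 20% | 0.30 × 0.8 = 24.0% | 0.24/0.94 = 25.5% |
| 30% | 50% | 0.30 × 0.5 = 15.0% | 0.15/0.85 = 17.6% |
| 15% | 20% | 0.15 × 0.8 = 12.0% | 0.12/0.97 = 12.4% |
| 15% | 50% | 0.15 × 0.5 = 7.5% | 0.075/0.925 = 8.1% |

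The dropped column applies only to assays not done. An assay done and found negative follows the first column. With m = 0 the reported rate equals r.

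**5. Cross-reference**

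Section 3.3.2.4 points to Table 3.3-4 and 7.2.2.4 to Table 3.3-3. The latter has no recurrence category, so 7.2.2.4 cannot be carried out as written.

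**The case against.** The strongest reply is that the loss need not be common. Stool collection and the toxin assay are scheduled at withdrawal, 7.1.7 excuses only what is refused or cannot be performed, and a patient with at least three unformed stools a day can usually provide a sample. Because a judgement that therapy is required is enough to trigger withdrawal, the sample can precede treatment and lie close to the episode. This stands. The plan allows events to be lost; it does not show that they will be.

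Second, analysis detail is left to a SAP that is not at hand. That is fair for tabulation rules. But the investigator makes the classification under Table 3.3-4, and no SAP can recover a stool that was never collected.

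Third, the endpoint is secondary and exploratory, and dose decisions rest on treatment-period data (3.1, criteria for dose escalation). This stands and limits the severity.

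A reader might infer more than the documents support:
- *That a relapse confirmed by PCR or colonoscopy can never count.* Entry does accept "A positive clinical laboratory result in one of the following methods to confirm CDI", including those two, so a patient may enter without a positive toxin assay. The relapse still counts if the central assay is positive, and a patient negative at entry may be positive later. With site-specific methods in an open-label trial, one central assay is a defensible common standard.
- *That the reported rate is a fixed fraction of the true one.* The share lost is unknown, and the simple product ignores the dropout route.
- *That the wrong table number biases the rate.* It is a clerical error with no direction.
- *That an advantage over existing drugs would be claimed.* The 15% to 30% is background, and no comparison with it is planned.

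**Conclusion.** The point holds in limited form. The protocol makes a positive central toxin result indispensable for recurrence, makes the withdrawal visit the usual place to obtain it, and lists recurrence as a reason for not obtaining it. It leaves open whether treated diarrhoea without that result is a cure or missing. Both readings lower the recurrence rate.

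The size is not derivable. At ten cures per dose, one lost event among three changes 30% to 20% or 22%. The wider range in the table rests on an assumed loss of 20% to 50% of recurrences. This should be fixed. It does not affect the dose decisions, and it does not show that the reported rate will in fact be wrong.

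**What to change.** 1. **Section 7.1.7.** State that the recurrence example does not cover the stool sample for the toxin assay. Ask for that sample, where feasible, before CDI therapy starts. This concerns only the collection of the sample, not whether or when therapy is given.
2. **Table 3.3-4 and 11.3.4.4.** Do not let a missing toxin result default to sustained cure, and do not drop such patients, including through the CPPS completeness rule. Keep them in the denominator and report new diarrhoea plus CDI therapy without a toxin result as its own category. Show patients who leave before FU2 separately, not as sustained cure. In the example above this gives 2/10 recurrences with 1/10 in the separate category.
3. **Sensitivity analysis.** Prespecify one that counts every patient with new diarrhoea plus CDI therapy as a recurrence whatever the toxin result; the example then gives 3/10.
4. **Section 7.2.2.4.** Change the reference from Table 3.3-3 to Table 3.3-4.

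**Cost.** A short amendment to four places. Diary stool records, concomitant therapies and central toxin results are already collected (7.2.2.6, 6.2, 7.2.2.2). The reported recurrence rate may be slightly higher. The sensitivity analysis rests on an open-label treatment decision, which is why it should accompany the toxin-confirmed definition and not replace it. Accepting site PCR or colonoscopy as confirmation, or moving to sustained cure over all treated patients, would be a different endpoint with its own trade-offs and is not needed to close this gap.
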